Webber, K. H., Tate, D. F., Quintiliani, L. M. (2008). Motivational interviewing in internet groups: a pilot

study for weight loss. *J Am Diet Assoc*, 108(6),1029-32.

West, D. H., Harvey, J. R., Kruckowski, R. A., Prewitt, T. E., Priest, J., & Ashikaga, T. (2016). Do individual online motivational interviewing chat sessions enhance weight loss in a group online weight control program? *Obesity*, 24(11), 2234-2340.

Westra, H. A., Aviram, A., & Doell, F. K. (2011). Extending motivational interviewing to the treatment of major mental health problems: Current directions and evidence. *Canadian Journal of Psychiatry*, 56(11): 643-650. Doi: 10.1177/070674371105601102

WHO ASSIST Working Group. (2002). The Alcohol, Smoking and Substance Involvement Screening Test (ASSIST): development, reliability and feasibility. *Addiction*, 97(9), 1183-1194.

Williams, J. K., Kisler, K. A., Glover, D., & Sciolla, A. (2011). *Exploring childhood sexual experiences and vulnerability to intimate partner violence among African American MSMW: Was that abuse or love?* New York: Nova Science Publishers.

Analysis Plan

To assess the success of randomization, baseline demographic and clinical characteristics, the two randomized groups were compared using chi-square tests for categorical variables and t-tests or Mann-Whitney tests for continuous variables. Data analyses were conducted on the intent-to-treat sample. All variables were evaluated for their distributional properties and data processing errors. Robust estimators were used to address non-normal data.

Variables were assessed for amount and pattern of missing data. Full information maximum likelihood estimation was used in subsequent analyses to address missingness. Inclusion of informative variables were included as needed. Analyses were conducted in SPSS 28.0 (IBM, 2021). For outcome analyses, linear mixed models (LMM) of mental health symptoms were modeled as a repeated measures outcome variable, nested within participants. Baseline demographic, clinical variables, and sexual abuse experiences were included as time-invariant covariates (between participants), as was treatment group. Thus, for each outcome, the primary analysis included all observations nested in persons and cohorts, controlling for baseline clinical and demographic variables.

Before examining the potential role of any mediators, LMM was conducted to determine any main or interaction effects condition and/or time may have had on these mediators as outcomes. To assess heterogeneity of treatment effects, the potential moderating impact that participant demographic variables and significantly correlated covariates had on the relationship between condition and primary outcomes was examined by including a moderator x condition interaction term in models.

Inclusion of demographic and clinical variables in mixed models allowed for testing of heterogeneity of treatment effects (HTE), with adjusted *p*-values. Specifically, in addition to the primary analyses, subsequent supplementary analyses tested potential moderators by including a treatment group X demographic interaction (race, comorbidity, and education) as these are the most likely candidates for HTE effects. Potential moderating effects of baseline values of minority stress, conformity to masculine norms and barriers to help seeking were also examined using SPSS PROCESS, which provides estimates of conditional effects of focal predictor (treatment condition) at different values of the moderator.

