Demographics and SGM Identification. Participants will be asked about their age, gender at birth, current gender identification, race/ethnicity, sexual orientation, marital status, highest level of education, and employment status at screening. Participants will also be asked about their treatment status to ensure eligibility (not currently in mental health treatment and/or have not been in treatment for past 60 days). Across post-interventions and follow-ups, participants will be asked if there are any changes to their employment, education, or marital status.

Sexual Abuse Characteristics. Participants will be asked about the age of onset of sexual abuse; type of abuse (e.g., penetration, non-penetration); number of perpetrators; relationship to their perpetrator(s); and the frequency of the abuse. Participants will also be asked if someone had found out about the abuse while it was occurring, and if they received any kind of psychotherapy or counseling as a result.

Current Experiences of Distress will be measured using the ***Center for Epidemiological Studies Depression Scale (CES-D; Radloff, 1977)***, a 20-item questionnaire that asks about experience and frequency of depressive symptoms over the past week. A score of 16 or higher identifies those individuals who are at risk for major depression. This score will be used as our cutoff for inclusion in the study.

Life Events Checklist (Blake et al., 1995) is a self-report measure that screens for 16 potentially traumatic events across individuals' lifetimes. Participants note whether the event happened to them personally, they witnessed it happen to someone else, they learned about it happening to someone close to them, or if it does not apply or does not fit.

MINI (Sheehan et al., 1998) is a structured interview that takes approximately 15-20 minutes to administer. The MINI is used extensively in research studies to make fairly quick and accurate diagnoses of psychiatric disorders and will be used here to assess, in part, for exclusion criteria.

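### Taken literally, fitting the symptom mixed models by full maximum likelihood with an uncounted block of between-person covariates makes arm-level standard errors about 1% to 8% too small; REML would avoid this

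*Combined protocol and SAP*

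**What the plan says.** The Analysis Plan, which follows the References, names one estimation method: "Full information maximum likelihood estimation was used in subsequent analyses to address missingness". The linear mixed models for symptoms come next. On covariates it states: "Baseline demographic, clinical variables, and sexual abuse experiences were included as time-invariant covariates (between participants), as was treatment group". It sums up the structure by saying that "the primary analysis included all observations nested in persons and cohorts, controlling for baseline clinical and demographic variables". It also says "Robust estimators were used to address non-normal data", without naming the type, and gives the software as SPSS 28.0.

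The covariates are described only as families. Section IV.3 (Research Plan, Screening) shows what is collected:

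- Demographics: "age, gender at birth, current gender identification, race/ethnicity, sexual orientation, marital status, highest level of education, and employment status", which is 8 variables, mostly categorical.
- Abuse history: "age of onset of sexual abuse; type of abuse (e.g., penetration, non-penetration); number of perpetrators; relationship to their perpetrator(s); and the frequency of the abuse", which is 5 items. The sentence after it adds 2 more (whether anyone found out, and whether counselling followed), making 7.
- Baseline clinical scales, listed under Outcomes and in Table 1.

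The documents do not mention REML or a small-sample degrees-of-freedom method. They give no count of coefficients, and they do not say whether the treatment test is the arm main effect, arm by time, or a difference at one visit.

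**The concern.** Arm is a between-person factor, so the standard error of its main effect rests on the between-person variance. In a mixed model, ML estimates that variance as if the fixed effects were known; REML allows for having estimated them. With many between-person covariates, ML is too small by a factor that grows with each one added. A moderator-by-condition term built from baseline variables is also a between-person contrast and has the same problem.

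The reason given for full ML is missing data, but that does not favour ML over REML. Both use every available outcome record under missing at random. The choice therefore gains nothing for missingness and biases arm-level error bars in one direction, toward intervals that are too narrow and tests that reject too often. CES-D depression is a stated primary outcome, so a main result could be affected if its treatment test is an arm-level contrast.

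**Working it through.** **The plan's own figures.** The plan states no standard error, variance or covariate count, so no stated figure tests this point directly. The sample sizes used below are 356 randomized (Section IV.3; Section V, item 3) and 274 completers (Section V, item 4, 2 × 137). The recruitment figure reproduces: 274 / 0.80 = 342.5, so 343, or 344 as an even number. The 137 per arm does not: an effect of .35, power .80 and two-sided .05 give 129 (normal) or 130 (t-test). That difference is on the conservative side and does not enter this check.

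**Arm main effect.** For balanced data with a random intercept per person, where *k* is the number of covariate coefficients and *p* = *k* + 2 (intercept and arm):

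SE(ML) / SE(REML) = √(1 − *p*/*N*)

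True level of a nominal two-sided .05 test ≈ 2 × [1 − Φ(1.96 × ratio)]

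Example with *k* = 22 and *N* = 274: √(1 − 24/274) = √0.9124 = 0.955, which is 4.5% too small. Then 1.96 × 0.955 = 1.872, for a true level of .061.

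| *k* (assumed) | *N* = 274: SE shortfall, true level | *N* = 356: SE shortfall, true level |
|---|---|---|
| 5 | 1.3%, .0530 | 1.0%, .0523 |
| 10 | 2.2%, .0553 | 1.7%, .0540 |
| 22 | 4.5%, .0612 | 3.4%, .0584 |
| 30 | 6.0%, .0655 | 4.6%, .0615 |
| 40 | 8.0%, .0713 | 6.1%, .0657 |

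The value 22 assumes one coefficient per variable: 8 demographic + 7 abuse + about 7 clinical. The value 40 allows for dummy coding. A 3% shortfall needs *p* = *N* × (1 − 0.97²) = 0.0591*N*, or about 16 coefficients in total at 274 and 21 at 356.

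**Arm by time.** The loss is within-person. With four visits it is 2 × 3 = 6 degrees of freedom out of 3*N*. The shortfall is 1 − √(1 − 6/822) = 0.37% at 274 and 1 − √(1 − 6/1068) = 0.28% at 356, whatever the number of between-person covariates.

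**Arm difference at one visit.** Assume within-person correlation .5 and three post-baseline visits. The between-person part of the variance is .5 + .5/3 = 2/3 of the total, so two-thirds of the variance shortfall carries over. With *k* = 22: 1 − √(1 − (2/3)(24/356)) = 2.3% and 1 − √(1 − (2/3)(24/274)) = 3.0%.

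**Simulation.** ML and REML fits were compared over 1,500 runs per setting (three post-baseline visits, correlation .5). Mean SE ratios for arm:

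- *N* = 356 with 20% dropout: 0.989, 0.982, 0.963 and 0.934 for *k* = 5, 10, 22 and 40.
- *N* = 274 complete: 0.955 and 0.920 for *k* = 22 and 40.

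The arm-by-time ratio was 0.997-0.998 throughout. A separate simulation with 36 or 44 therapy groups, intraclass correlation 0 to .05 and 15 or 30 covariates gave 0.934 to 0.968 for arm.

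Simulated rejection rates carry a Monte Carlo error of about √(.05 × .95/1500) = 0.6 percentage points. With 22 covariates they do not separate clearly from .05; with 40 they were .072-.074 under ML against .055-.058 under REML. The SE ratios are the firmer evidence.

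**The case against.** A reader might infer that every interval for CES-D and the secondary scales is several percent too narrow. The documents do not support that, for five reasons:

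- **The count is unknown.** The Screening lists show what is collected, not what is entered. For moderators the plan speaks of covariates that correlate significantly, so a short list is possible. With 5-10 coefficients the shortfall is only 1.0-2.2%.
- **The contrast is unnamed.** The aim is phrased in terms of symptom change, and for mediators the plan tests both main and interaction effects of condition and time. If the treatment test is arm by time, the shortfall is negligible.
- **The quoted sentence concerns missingness.** It may be loose wording for using all available data, and the variance components may have been estimated by REML.
- **Robust estimators are mentioned.** Their type is not given, so they can be neither counted as a cure nor ruled out as one.
- **Scope.** Treatment engagement is binary, and the mixed models are described for symptoms. Minority stress, masculine norms and barriers to help seeking were examined as moderators with PROCESS.

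All five stand as limits on size and reach. None removes the point: as written, the method is full ML, and its stated reason does not favour it over REML. Nor does the result depend on using completers only or on ignoring groups. The range at 356 is still 1.0-6.1%, and the simulation with therapy groups gave similar ratios.

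**Conclusion.** The point holds in a limited form. If the models were fitted as the Analysis Plan literally says, standard errors for arm main effects and between-person moderator-by-condition terms are too small by about 1-2%, 3-5% or 6-8% with 5-10, about 22 or about 40 covariate coefficients. The corresponding true levels are about .052-.055, .058-.061 and .066-.071. These figures rest on assumed covariate counts, model-based standard errors, *N* between 274 and 356, and two-sided tests (the plan does not state sidedness). Single-visit arm differences carry part of the shortfall; arm-by-time contrasts carry under 0.5%. The effect is modest and would matter mainly for a borderline result. It is not shown that any particular reported interval is wrong, and the engagement outcome is untouched.

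**What to change.** Fit the symptom, mediator and mixed-model moderator analyses by REML with Satterthwaite or Kenward-Roger degrees of freedom. Keep full ML only for likelihood-ratio comparison of models with different fixed effects. Replace the missing-data sentence with one saying that missing outcomes are handled by the REML likelihood under missing at random, the same assumption as now. If REML was in fact used, that sentence alone settles the matter. Listing the covariates with their number of coefficients, and naming the treatment contrast, would let a reader see how much was at stake.

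The cost is one estimation setting, a few sentences and slightly wider intervals. No participants or data are lost. The Analysis Plan is written in the past tense, so where results already exist the models can be refitted and any changed conclusion reported.

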We will conduct a randomized comparative effectiveness trial of peer-facilitated, online, 6-week group MI vs. MI with a trauma-informed SGM affirmative care approach. Randomization will be counterbalanced by treatment status: treatment naive versus treatment-experienced (prior treatment not within the past 60 days). Randomization will be based on a list of computer-generated random numbers. We will randomize 356 SGM male trauma survivors to either condition. Assessments will occur at baseline, post-intervention, and at 60- and 120-day follow-ups, from the end of the intervention.

Comparators. Traditional MI will be compared to MI with trauma-informed SGM affirmative care (MI+). Groups will take place 1.5 hours once a week for 6-weeks and will be led by two peer specialists trained in MI or tailored MI. Groups will consist of approximately 8-10 members and be closed for the duration of the group. It is anticipated that new groups will begin every other month (allowing for a two week break between groups) to reduce burden on peer specialists and supervisors.

Traditional MI groups. Six traditional MI groups will take place for 1.5 hours online facilitated by two peer specialists.

Trauma-informed, SGM+ affirmative care MI groups. Six tailored MI groups will take place for 1.5 hours online facilitated by two peer specialists. Please see Appendix A for a detailed overview and outline of the major supplemental MI modules aimed at SGM minority stress, traditional masculinity, and male sexual abuse.

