Fidelity monitoring will occur ad hoc by independent raters using audio-recordings of intervention sessions. At least 30% of the sessions (traditional MI and trauma-informed MI) will be coded ($n = 90$). Three coders will rate each session. [name] will host a training with the raters to familiarize them with the rating scales and interventions. The three raters will conduct the fidelity ratings over a six to eight month period (approximately) between June 2021 and February 2022. The three raters ([name], [name] and [name]) have previous experience conducting this task and will be supervised by [name]. Audio recordings of selected group sessions will be sent to the raters using Yale's secure file transfer (FileLocker).

Assessment Measures. Peer specialists will also be asked to complete a reflective journaling exercise (see attached) after each treatment cycle they co-facilitate. In addition, they will complete several assessments measures (see attached) prior to their attendance at the MI training then again after they attend the MI training. Peer specialists will be asked to answer approximately three open-ended questions at the end of the study.

Table 1: Assessment Schedule

Assessment Name		Screening	Baseline	Post-intervention	60-Day Follow-up	120-Day Follow-up
Peer Specialists	Independent Tape Rater Scale			x		
Male Survivors	Demographic and SGM identification	x	x	x	x	x
	Sexual abuse characteristics	x				
	Life Events Checklist	x				
	Mini International Neuropsychiatric Interview	x				
	Telephone-Assessed Mental State (TAMS)	x				
	Columbia-Suicide Severity Rating Scale (C-SSRS)	x	x	x	x	x

Brief Dissociative Experiences Scale (DES-B Modified for DSM-5)		x	x	x	x
Center for Epidemiological Studies-Depression Scale	x	x	x	x	x
PTSD Checklist for DSM-5		x	x	x	x
Alcohol Smoking and Substance Involvement Screening Test (ASSIST)		x	x	x	x
Inventory of Psychosocial Functioning		x	x	x	x
Barriers to Help Seeking Scale		x	x	x	x
Conformity to Masculine Norms Inventory		x	x	x	x
Minority Stress Scale		x	x	x	x
Working Alliance Inventory			x		
Service Use and Resource Form (SURF)	x	x	x	x	x
Adult Resilience Measure – Revised (ARM-R)		x	x	x	x

Participant Population: Provide a detailed description of the types of participants who will be recruited into this study.

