a. Targeted for enrollment at Yale for this protocol: 356 for the online groups.

b. If this is a multi-site study, give the total number of participants targeted across all sites.

4. How was this estimate derived?

Because this study examines repeated measures outcomes with the two treatment conditions, assigned at the individual level, power analysis makes several assumptions: continuous outcomes, a linear link function, random effects covariance structure, and homogeneous covariance structure (within treatment groups). These analyses also assume testing for HTE effects. Conservatively assuming an effect size of .35, with a power of .80 and an alpha of .05, 137 subjects per group would be required. This represents a total completed sample of 274. Assuming a dropout rate of 20% (rounded up to 70, for nearest multiple of 2), this requires a recruited sample of at least 344. In a meta-analysis of 72 clinical trials, the initial effect size, that is 1-month post-intervention, was quite high ($d = .77$). However, the strength of the effect decreased over time, with effect sizes of .39 at 1-3 months, and .31 at 6-12 months.

5. Process of Consent/Accent (*NOTE: When a study includes minors, parent provide permission [not consent] for the child's participation, and the child provides assent for participation*)

Informed consent is an ongoing process that is best suited by transparency and openness to participants. Thus, participants will give consent in the initial online screening contact form and verbally in the screening call. Participants will be provided with information about the nature of the study, as well as the expected time and energy commitment required to complete the assessments. It will also be explained to participants that they are consenting to be randomly assigned to one of two MI interventions (with brief explanation about content as well as frequency and length of sessions).

Participants will be asked to provide informed consent online, prior to completing in the screening questionnaires. Consent will be required in order to access the assessment measures. If a participant does not provide consent, they will not engage in the screening assessment or be enrolled in the study.

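### The mixed model for CES-D and the symptom scales does not settle the role of baseline or name a time term or contrast; read literally, its treatment coefficient is 25% below the average post-baseline effect

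*Combined protocol and SAP*

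**What the plan says.** The Outcomes section makes CES-D a primary outcome. It gives the other primary outcome, treatment engagement, a 120-day window, but gives CES-D no analysis time point. Table 1 lists the "Center for Epidemiological Studies-Depression Scale" at screening, baseline, post-intervention, 60 days and 120 days.

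The Analysis Plan at the end of the document treats symptom scores as a repeated measures outcome within participants. On covariates and treatment it says: "Baseline demographic, clinical variables, and sexual abuse experiences were included as time-invariant covariates (between participants), as was treatment group". It then sums up: "Thus, for each outcome, the primary analysis included all observations nested in persons and cohorts, controlling for baseline clinical and demographic variables".

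Time appears in that section only in connection with mediators: "LMM was conducted to determine any main or interaction effects condition and/or time may have had on these mediators as outcomes". No such sentence exists for CES-D, PCL-5 or the other symptom scales.

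The Research Plan states: "Randomization will be counterbalanced by treatment status: treatment naive versus treatment-experienced". The Analysis Plan does not name this factor as a covariate. It may be covered by the demographic variables, because treatment status is asked under the Demographics heading at screening, but nothing says so.

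**The concern.** Four things fix what a longitudinal treatment coefficient estimates: which visits are outcome rows, how the outcome's own baseline value enters, whether time and arm-by-time are in the model, and which contrast is reported. The text gives a partial and ambiguous answer to the first two and none to the last two for the symptom scales.

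The text permits at least these fits:

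- **Post-baseline rows only, own baseline score as covariate.** The group coefficient is the average post-baseline difference.
- **Baseline row kept, arm-by-time included.** The effect sits in the interaction terms. With baseline as the reference visit, the group coefficient is only the chance baseline difference.
- **Baseline row kept, single time-invariant group term.** The coefficient mixes the three post-baseline differences with a visit that precedes any intervention. Adding a main effect of time does not change this.

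The third is the literal reading, since every observation is said to be included and treatment group is entered only as a time-invariant term. It pulls the estimated difference between tailored and traditional MI towards zero for a primary outcome. A reader of the results could not tell which quantity had been reported.

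**Working it through.** **Inputs.** From Section V, item 4: effect .35 SD, alpha .05, power .80, "137 subjects per group would be required", 20% dropout, and a "random effects covariance structure". From the Research Plan: one baseline and three post-baseline assessments. Assumed here: two-sided test, the same .35 at each post-baseline visit, unit variance, and within-person correlation r = .3, .5 or .7, because the documents give no value.

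**The plan's own figures.** A simple two-sample comparison with d = .35 needs 2 × (1.96 + .84)² / .35² ≈ 128.1, so 129 per arm; 137 per arm gives power .826. Section V also cites repeated measures and heterogeneity testing without inputs, so 137 cannot be called wrong, and nothing below depends on how it was reached. The dropout step reproduces: 274 / .80 = 342.5, so 343, and 344 as the next even number.

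**Size of the coefficient, complete data.** Under compound symmetry (a random intercept), the single group term weights the four rows equally:

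- (0 + .35 + .35 + .35) / 4 = .75 × .35 = .2625, which is 25% below .35 for any r.
- Post-baseline rows only: (.35 + .35 + .35) / 3 = .35.

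**With dropout.** Under maximum likelihood, participants with few or no follow-up scores still contribute their baseline row. Each row of a person with m rows has weight 1 / (1 + (m − 1)r), so the share on the baseline row is E[1 / (1 + (m − 1)r)] / E[m / (1 + (m − 1)r)].

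- Assumed graded loss of 7%, 14% and 20% at the three visits (m = 4, 3, 2, 1 in 80%, 6%, 7%, 7%). For r = .5: (.320 + .030 + .047 + .070) / (1.280 + .090 + .093 + .070) = .467 / 1.533 = .304. For r = .3 and .7 the share is .295 and .313.
- If all 20% leave with a baseline row only, for r = .5: (.8 × .4 + .2) / (.8 × 4 × .4 + .2) = .52 / 1.48 = .351. For r = .3 and .7: .330 and .372.

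The coefficient is therefore about 30% below in the first case and 33 to 37% below in the second.

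**Check by simulation.** Random-intercept fits to 3,000 simulated participants, r = .5, true effect 1:

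| Fit | Complete data | 20% with baseline only |
|---|---|---|
| Post-baseline rows, baseline covariate | 1.015 | 1.015 |
| Equal baseline means imposed | 1.015 | 1.024 |
| Four rows, single group term | .748 | .642 |
| Same, baseline also a covariate | .761 | .695 |

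With arm-by-time and complete data, the group coefficient was −.022 and the three interaction terms were 1.049, 1.021 and 1.007.

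**Power without the own baseline score as covariate.** The standard error is √(2v / 137), with v = (1 + 2r)/3 for three rows and (1 + 3r)/4 for four.

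| r | v, three rows | .35 / SE | Power | v, four rows | .2625 / SE | Power |
|---|---|---|---|---|---|---|
| .3 | .533 | 3.97 | .98 | .475 | 3.15 | .88 |
| .5 | .667 | 3.55 | .94 | .625 | 2.75 | .78 |
| .7 | .800 | 3.24 | .90 | .775 | 2.47 | .69 |

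**Power with the own baseline score as covariate in both fits.** The four-row mean equals .25 × baseline + .75 × post-baseline mean. Once baseline is adjusted for, the coefficient and its standard error are each exactly .75 times their post-baseline counterparts. For r = .5 the residual variance is .667 − .25 = .417 for three rows and .625 − .625² = .234 for four, and .75² × .417 = .234. The test statistic is the same, and power is .99 or more in both fits at every r.

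**The case against.** The strongest reply is that the plan is not silent. It says that all observations are used and that baseline clinical variables are controlled for. An experienced analyst could take this as post-baseline scores adjusted for baseline CES-D, which is sound and undiluted. That reading is available, so the defect is ambiguity on rows and baseline. But the sentence does not say that the scale's own baseline score is one of the clinical variables, and including all observations points the other way. The missing time terms, contrast and visit have no answer elsewhere in the document.

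A second reply is that significance is unaffected. This stands wherever baseline CES-D is a covariate in both fits: with complete data the p-values are the same. A reader might infer that the choice of fit generally costs power or changes the verdict. The text does not support that, because one covariate rule covers every outcome; the loss arises only if the own baseline score is left out. Nor is there a false-positive problem for any one pre-stated fit, since under no effect the arms are equal at every visit.

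A reader might also infer from Table 1 that the screening CES-D is an outcome row, with more dilution. The documents speak against this. The Research Plan lists assessments from baseline onwards, the outcomes are headed as baseline, post-intervention and follow-up measures, and the screening score serves as the inclusion cutoff.

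**Conclusion.** The concern holds as an under-specified analysis of a primary outcome whose literal reading gives an estimate biased towards zero. That fit returns .75 of the average post-baseline effect: .26 for a true .35. The 25% assumes four rows, complete data and compound symmetry, the last in line with the random-effects assumption in Section V. It becomes about 30% or more with dropout under the loss patterns assumed above.

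The power figures of .88/.78/.69 against .98/.94/.90 rest on assumed correlations, 137 per arm and a constant effect, and apply only if the own baseline score is not a covariate.

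It would go too far to conclude that the diluted fit was the one run. The document does not say so; it only fails to exclude it. The point does not concern the binary engagement outcome. It should be fixed, and confidence is medium because the text allows a sound reading.

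**What to change.** State in the Analysis Plan, for CES-D and each symptom scale:

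1. **Rows and baseline.** Post-baseline scores are the outcome and the same scale's baseline score is a covariate. Alternatively, use a constrained longitudinal model with equal baseline means in the two arms.
2. **Terms.** Arm, time, arm-by-time and, by name, the treatment-naive/treatment-experienced randomisation factor.
3. **Contrast.** One for CES-D: either the average post-baseline difference, which suits the repeated-measures basis of the sample size, or one named visit. Report the per-visit differences as well.
4. **Disclosure.** The plan is written in the past tense, so say which fit was run and whether its contrast was chosen after data were seen. Re-fit if a baseline row with a single group term was used.

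The cost is a paragraph of text, a few more parameters per model and possibly a re-fit. No new data are needed.
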